9.4.3 Assessment of adequacy of hemostasis during minor surgical interventions

Pre-study medication used for minor surgery will be recorded on the CRF. The doses administered and the frequency of any treatment will be collected.

The investigator, surgeon, or interventionalist will be asked to compare estimated blood loss from experience with non-hemophilic subjects undergoing comparable procedures, and assess intraoperative efficacy at the end of the procedure ([Table 9–6](#)). Post-surgical efficacy will be assessed at least 24 h after the end of the procedure by the investigator or surgical staff at drain removal, if required, and by the investigator or hematologist at discharge.

Table 9–6 Criteria for the assessment of efficacy in minor surgery (5)

Excellent	Intra-operative and post-operative blood loss similar (within 10%) to the non-hemophilic patient. 
• No doses of FVIII/FIX/bypassing agents needed AND• Blood component transfusions required are similar to non-hemophilic patient
Good	Intra-operative and/or post-operative blood loss slightly increased over expectation for the non-hemophilic patient (between 10-25% of expected), but the difference is judged by the involved surgeon/anesthetist to be clinically insignificant. 
• No doses of FVIII/FIX/bypassing agents needed AND• Blood component transfusions required are similar to the non-hemophilic patient
Fair	Intra-operative and/or post-operative blood loss increased over expectation (25-50%) for the non-hemophilic patient and additional treatment is needed. 
• FVIII/FIX/bypassing agents needed OR• Increased blood component (within 2 fold) of the anticipated transfusion requirement
Poor/none	Significant intra-operative and/or post-operative blood loss that is substantially increased over expectation (>50%) for the non-hemophilic patient, requires intervention, and is not explained by a surgical/medical issue other than hemophilia 
• Unexpected hypotension or unexpected transfer to ICU due to bleeding OR• Substantially increased blood component (> 2 fold) of the anticipated transfusion requirement

Data on blood loss will be collected, as estimated at the time of surgery, change or drop in hemoglobin/hematocrit, the need for additional or other hemostatic medications, and the type and number of blood products transfused. Hemostatic-related surgical complications will also be obtained including data on specific diagnostic evaluations needed (example: Imaging to follow size of a hematoma).

9.4.4 Hemophilia joint health score (HJHS)

The HJHS score will be evaluated at the start of treatment and the final visits.

The HJHS measures joint health in the domain of body structure and function (i.e., impairment) of the joints most commonly affected by bleeding in hemophilia: Elbows (left/right), knees (left/right), ankles (left/right).

Items to be assessed per joint: Swelling, duration (swelling), muscle atrophy, crepitus on motion, flexion loss, extension loss, joint pain, and strength.

The possible range per joint is 0-20 score points, where 0 denotes the best possible and 20 the worst joint status. Thus, the sum for all 6 joints is 120 score points at maximum. In addition, general gait is to be assessed: 0-4 score points.

The HJHS total score is the sum of the 6 joint scores plus the score for general gait and ranges from 0 to 124 score points.

9.5 Pharmacokinetics/pharmacodynamics

9.5.1 Pharmacokinetics

9.5.1.1 Drug measurements

Blood samples for PK analyses of BAY 1093884 (anti-TFPI mAb) in plasma will be collected at the time points given in the study flow chart (see [Table 9-1](#)).

Plasma concentrations of BAY 1093884 will be measured using a validated ligand binding assay method. Quality control (QC) and calibration samples will be analyzed concurrently with study samples. The results of calibration, QC, and study samples will be reported in the bioanalytical report, which will be included in the clinical study report for this study.

Samples should be collected as close as possible to the nominal sample collection time. The actual sampling time should be documented on the eCRF pages and actual sampling time will be used when calculating the pharmacokinetic parameters. Deviations from planned PK blood sampling times are not considered as protocol violations. In the case of missing records of the actual sampling times, planned sampling times may be used for PK evaluation.

Information on the collection, processing, storage and shipment of biomarker samples will be provided in a separate document.

In case a subject bleeds during the period of dense sampling for PK, subject must treat the bleed and continue PK sampling with no modifications to the PK sampling schedule.

9.5.1.2 Pharmacokinetic evaluation

Non-compartmental analysis

PK parameters will be calculated using the model-independent compartment-free method according to the current Bayer guidelines using the PK software WinNonlin, version 5.3 or higher. Based on the concentration time data, the following PK parameters will be calculated:

BAY 1093884 in plasma

Main PK parameters: $AUC(0-t_{last})$, $AUC(0-t_{last})/D$, C_{max} , C_{max}/D

Additional parameters: Optionally AUC , AUC/D , $t_{1/2}$, V_{ss} , CL , MRT , V_z , $\%AUC(t_{last-\infty})$, points terminal may be estimated. Normalization of AUC to dose and/or body weight may be performed.

For multiple dose administration, the following parameters may also be estimated in addition to the parameters listed as main PK parameters:

After the first dose: AUC_{0-7d} , AUC_{0-7d}/D , C_{max} , C_{max}/D

After the last dose: $AUC_{\tau,md}$, $AUC_{\tau,md}/D$, $C_{max,md}$ and $C_{max,md}/D$, and accumulation ratios ($RA_{C_{max}}$, RA_{AUC})

Additional PK parameters may also be estimated.

In addition, data obtained from this study may be subject to PK modeling and simulation.

Details of the model development and evaluation will be described in a separate Evaluation Plan and the results reported in a separate Evaluation Report.

9.5.2 Pharmacodynamics and biomarkers

Pharmacodynamic parameters will include:

- PT, aPTT, D-dimer, fibrinogen, FV level (clotting assay), antithrombin activity, protein C activity, thrombin generation assay (TGA/CAT PPP), TFPI activity (chromogenic), total (i.e., LDL-devoid and LDL-bound) TFPI concentration in plasma, FVIIa, dPT (dilute PT), prothrombin fragment 1 and prothrombin fragment 2 (F1+2), thrombin-antithrombin complex (TAT)

Optional pharmacodynamic parameters (locally, if specific instrument is available):

- Thrombelastometry/thrombelastography (ROTEM/TEG)
- Thrombin generation assay (TGA/CAT PRP)

CCI

[REDACTED]

Procedures for processing, shipping and analysis of samples will be described in a separate manual.

9.6 Safety

Safety variables:

- Incidences of drug-related AEs, SAEs, adverse events of special interest (AESIs), injection site reactions (ISRs) and clinically relevant^a abnormal laboratory values.
- Incidences of binding and neutralizing antibodies against BAY 1093884

Safety measures will include:

- AEs/SAEs/AESIs and ISRs by

^a “Clinically relevant” implies the presence of a clinical sign or symptom that requires medical action.

- Relationship to study drug
- Severity
- AEs leading to discontinuation of study drug
- Anti-TFPI antibodies (immunogenicity)
- Clinical laboratory data including:
 - CBC with differential count and platelets
 - Serum chemistry
- Vital signs
- Evaluation of concomitant medication
- Physical examination

9.6.1 Adverse events

Please note:

Any bleeding event occurring during the study will not be documented as an AE, because this event is captured in the assessment of efficacy. However, if the bleed requires hospitalization or fulfills another seriousness criterion, it must be reported as an SAE (see Section 9.6.1.3.1).

Please note:

Any thromboembolic or thrombotic microangiopathic event is an AESI and will be considered to be an SAE (see Section 9.6.1.4). Any thromboembolic or thrombotic microangiopathic event will be sufficient to require a review of safety by the DMC (see Section 13.1.2). Dosing will be suspended in the affected subject(s) until consultation with the DMC (see Section 9.6.1.7).

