9.4.1 Electronic patient diary (EPD)

Treatment logs are commonly used for hemophilia subjects for documentation of their home treatment. Home treatment and bleeding information are the key variables evaluated in this study. Study specific treatment logs will be provided in national language. The preferred system for this study will be EPD devices since they are interactive, allow for real time data transmission, record-stamp date and time of fulfillment, and facilitate the clarification of data with the site and during the data cleaning process. Subjects or their caregivers will be provided with EPDs for the whole study. At Screening visit, subjects and caregivers will be trained in the use of the device. These logs will be used to collect the treatment data and bleeds by the caregivers or subjects, and the data will be verified for accuracy and completion by the investigator or delegate during regularly scheduled interactions with the subject or caregiver. Thus, the EPD will be considered the source for these data.

For each self-administered injection of study drug, information must be recorded on the EPD as follows:

Each injection of BAY 1093884

- Date and time [24 hour clock]
- Individual vial number (bar code scan from vial label)
- Number of vials used
- Volume in mL that was injected

Injections of study drug as part of protocol-mandated visits and procedures will be recorded on the respective CRF pages.

All bleeding episodes (regardless if treated or not, or treated at home or under medical supervision) as well as the potential treatment with pre-study hemophilia drugs will be recorded in the EPD:

Bleeding episode (onset)

- Date and time [*24 hour clock*] of onset
- Type of bleed [*spontaneous, non-spontaneous/non-traumatic, traumatic*]
- Location [*joint, muscle, skin or mucosa, internal, other; body map*]
- Intensity [*mild, moderate, severe*; according to subject's own judgment]
- Treated [*yes/no*];
if "yes": Date and time [*24 hour clock*]
 Product class used
 Number of injections, doses

9.4.2 Dose of pre-study hemophilia medication administered and number of injections needed to stop a bleeding event

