However, it should be noted that invasive treatment during any hospitalization may fulfill the criterion of ‘medically important’ and as such may be reportable as an SAE dependent on clinical judgment. In addition, where local regulatory authorities specifically require a more stringent definition, the local regulation takes precedence.

- d. Results in persistent or significant disability/incapacity

Disability means a substantial disruption of a person’s ability to conduct normal life’s functions.

- e. Is a congenital anomaly/birth defect
- f. Is another serious or important medical event as judged by the investigator

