9.6.1.2.3 Causal relationship

The assessment of the causal relationship between an AE and the administration of treatment is a decision to be made by the investigator, who is a qualified physician, based on all information available at the time of the completion of the eCRF.

The assessment is based on the question whether there was a “reasonable causal relationship” to the study treatment in question.

Possible answers are “yes” or “no”

An assessment of “no” would include:

1. The existence of a highly likely alternative explanation (e.g., mechanical bleeding at surgical site)

or

2. Non-plausibility (e.g., the subject is struck by an automobile) when there is no indication that the drug caused disorientation that may have caused the event; cancer developing a few days after the first drug administration.

An assessment of “yes” indicates that the AE is reasonably associated with the use of the study treatment.

Important factors to be considered in assessing the relationship of the AE to study treatment include:

- The temporal sequence from drug administration: The event should occur after the drug is given. The length of time from drug exposure to event should be evaluated in the clinical context of the event.
- Recovery on drug discontinuation (de-challenge), recurrence on drug re-introduction (re-challenge): Subject's response after de-challenge or re-challenge should be considered in view of the usual clinical course of the event in question.
- Underlying, concomitant, intercurrent diseases:
Each event should be evaluated in the context of the natural history and course of the disease being treated and any other disease the subject may have.
- Concomitant medication or treatment:
The other drugs the subject is taking or the treatment the subject receives should be examined to determine whether any of them might have caused the event in question.
- Known response pattern for this class of drug: Clinical/preclinical
- The pharmacology and pharmacokinetics of the study treatment:
The pharmacokinetic properties (absorption, distribution, metabolism and excretion) of the study treatment, coupled with the individual subject's pharmacodynamics should be considered.
- The assessment is not possible

Causal relationship to protocol-required procedure(s)

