9.6.1.6 Dose-limiting toxicities

Dose-limiting toxicities (DLTs) are defined as any of the following events that are clearly unrelated to underlying disease and occurring at any dose level.

- Presence of any symptoms or signs of TE or TMA
- Platelets <100 giga/L or fibrinogen <100 mg/dL at any visit
- Any grade ≥ 3 according to CTCAE criteria version 5.0 (CTCAE criteria do not apply for toxicities related to underlying disease like aPTT)
- Grade ≥ 2 toxicities according to CTCAE criteria in case of symptoms of disseminated intravascular coagulation (DIC) or hemolysis

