6.4.1 Adverse events

The investigator has to record on the respective CRF pages all adverse events occurring in the period between the signing of the informed consent form and the end of the follow-up phase. The original terms used by investigators to report AEs via the CRFs will be coded using the Medical Dictionary for Regulatory Activities (MedDRA).

For each AE, the number and percentage of subjects who experienced at least 1 occurrence of the given event will be tabulated according to the affected primary system organ class (SOC) and preferred term (PT) by dose cohort and dose actually received. A total column will be included in all safety summaries.

Frequency tables, showing an overall summary of number of subjects with drug-related AEs, SAEs and AESIs will be given, and will include the following information:

- maximum intensity for any AE,
- AE related deaths,
- AE resulting in permanent discontinuation of study drug,

- treatment emergent AE.

AEs will be considered treatment-emergent if they begin after the first administration of study drug and they do not start after more than 30 days after the last administration. Determination of whether or not an event is treatment-emergent will be derived after the missing or incomplete AE start date is imputed. Inhibitors will be defined as treatment-emergent if they develop after first study drug application. Imputation rules for missing and incomplete AE start are described in section 4.3.

The severity or intensity of an AE should be graded according to the National Cancer Institute Common Terminology Criteria for Adverse Events (NCI CTCAE) version 5.0. If no exact matching code is available in NCI CTCAE version 5.0, the following guidance should be used:

- CTCAE grade 1: Mild
- CTCAE grade 2: Moderate
- CTCAE grade 3: Severe and/or disabling AE
- CTCAE grade 4: life-threatening and/or intervention needed
- CTCAE grade 5: resulting in death (fatal)

A similar table showing overall summary information of AEs during screening will be given.

In addition, frequency tables will summarize the number of subjects with injection site reactions.

Similar to 6.2, frequency tables will summarize the number of subjects with

- any event during Part A,
- any event during each 12-week Part B period
- any event during combination of these periods.

This will also include tabulation by dose actually received.

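### Section 9.6.1 keeps every non-serious bleed out of AE documentation whatever its cause or site, so drug-related and injection-site bleeds can be missing from the safety incidences

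*Protocol*

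**What the plan says.** Protocol Section 9.6.1 opens with a rule for bleeds: "Any bleeding event occurring during the study will not be documented as an AE, because this event is captured in the assessment of efficacy". The next sentence gives the only exception: "However, if the bleed requires hospitalization or fulfills another seriousness criterion, it must be reported as an SAE". The seriousness criteria in Section 9.6.1.1 end with a judgment item: "Is another serious or important medical event as judged by the investigator".

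Section 9.4.1 sends all bleeds, treated or untreated, to the electronic patient diary. The fields listed there are onset, type, location, intensity in the subject's own judgment, and treatment.

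Section 10.3 makes the frequency of drug-related AEs part of the primary endpoint. ISRs are a named safety variable in Protocol Section 9.6 and SAP Section 6.4. The SAP handles them in its AE section, where "frequency tables will summarize the number of subjects with injection site reactions". Neither document defines an ISR or says where bleeding, bruising or hematoma at the injection site belongs.

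**The concern.** The rule sorts bleeds by seriousness alone. Its stated reason, that efficacy already counts the event, makes sense for a bleed caused by hemophilia. It does not fit a bleed that the investigator attributes to the study drug, or a bleed caused by the needle. BAY 1093884 acts on coagulation, is injected subcutaneously every week, and is tested in a trial whose primary objective is safety and tolerability. If such events are filed only as bleeds, they are reported as bleeding outcomes and not as tolerability. A DMC trigger that counts drug-related AEs would not see them either.

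**Working it through.** The documents state no figure on this point, so the check is mainly a comparison of sections.

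1. **What each route records.** An AE is assessed under Section 9.6.1.2 for seriousness, CTCAE grade, causal relationship (yes or no), action taken and outcome. The diary fields in Section 9.4.1 include no relatedness question, no CTCAE grade and no injection-site category. A non-serious bleed is therefore recorded, but without a causality answer or a grade.

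2. **Drug-related AE count.** The Section 10.3 endpoint needs an AE judged related. A non-serious bleed is not an AE under Section 9.6.1, so it cannot be counted, whatever the investigator thinks of its cause.

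3. **DMC trigger.** Section 9.6.1.7 item 1a has two limbs: one drug-related SAE, or two drug-related AEs that are severe or clinically significant. A non-serious bleed can reach neither.

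4. **Dose-limiting toxicities.** Section 9.6.1.6 asks whether an event is unrelated to the underlying disease. It uses CTCAE grade 3 or higher in general, and grade 2 or higher "in case of symptoms of disseminated intravascular coagulation (DIC) or hemolysis". For a bleed held only in the diary, neither the judgment nor the grade is recorded.

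5. **Other AE text.** Section 9.6.1.1 makes conditions that begin or worsen after consent AEs, with no carve-out for bleeds. Section 9.6.1.2.3 uses a surgical-site bleed as its example of an alternative explanation. Section 9.6.3.2 sends abnormal examination findings to medical history or AEs. Section 9.6.1 does not say how it relates to these.

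6. **Injection site.** A site that reads Section 9.6.1 literally logs an injection-site hematoma as a diary bleed. A site that reads it as covering hemophilic bleeds only reports an ISR. The ISR incidence then depends on each site's reading.

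7. **Scale.** Inputs are 8 subjects per cohort, 24 planned and 40 at most (Protocol Section 5). If a subject's only ISR is an unrecorded injection-site bleed, incidence falls by 100/n percentage points: 100/8 = 12.5, 100/24 = 4.2, 100/40 = 2.5. The plan uses exact 90% intervals for responder proportions. Applying that level to safety is an assumption made here for scale. For n = 8 the Clopper-Pearson interval is 0 to 31.2% with 0 events and 0.6% to 47.1% with 1 event. One misfiled subject moves the upper limit by 47.1 − 31.2 = 15.9 points.

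8. **Bleeding rate.** The bleed counts in SAP Section 6.2 are limited to bleeds that need treatment. An untreated injection-site bleed is outside them. It can reach the all-bleeds counts and annualized bleeding rate (ABR) in Section 1 of the additional SAP of 10 March 2020, which include untreated bleeds and show treated and untreated separately.

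**The case against.** The strongest reply is that most of what matters is captured elsewhere. Much of this stands.

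- A reader might infer that drug-related bleeding can never become a drug-related AE. The documents do not support that. Serious bleeds are SAEs, including those an investigator judges medically important, and Section 9.6.1.3 requires a separate sponsor causality assessment for each. One drug-related SAE is enough for the trigger. The gap is confined to non-serious bleeds.
- A reader might infer that toxicity through TMA, low platelets or low fibrinogen goes unseen. It does not. Section 9.6.1 makes every TMA event an AESI and an SAE, and Section 9.6.1.6 makes platelets below 100 giga/L or fibrinogen below 100 mg/dL a dose-limiting toxicity. What is missing is the grade and causality of the bleed itself, not detection of the condition.
- A reader might see a contradiction with Section 9.6.1.2.3. It is a tension only, because the surgical-site example could be a serious bleed.
- A reader might conclude that injection-site bleeding is zero in the ISR table by construction. That holds only if every site reads Section 9.6.1 literally. Section 7.1.2 describes bleeds as a manifestation of hemophilia, which suggests that hemophilic bleeds were meant.
- A reader might put a size on it. If p = 1% to 5% of 12 weekly injections bled, independently, 1 − (1 − p)^12 gives 11% to 46% of subjects, and 12p × 365.25/84 adds 0.5 to 2.6 bleeds per year to an all-bleeds ABR. The arithmetic is right, but p and independence are assumptions with no source in the documents. This is an illustration, not an estimate.

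It is also fair that the diary keeps a record of each bleed, that the investigator reviews it, and that ISRs are not a component of the primary endpoint. Individual dose escalation counts only spontaneous bleeds needing treatment, so untreated injection-site bleeding does not affect it. None of this supplies a causality answer for a non-serious bleed, or says how injection-site bleeding is to be classified.

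**Conclusion.** The point holds for non-serious bleeds. As written, a non-serious bleed judged drug-related is outside the drug-related AE frequency and outside the drug-related-AE limb in Section 9.6.1.7. This follows from the text without further assumption. The loss from the ISR incidence is conditional: it occurs where a site treats injection-site bleeding as a bleeding event under Section 9.6.1. Each affected subject with no other ISR is then worth 12.5 percentage points in a cohort of 8. How many subjects that would be is unknown. Untreated injection-site bleeding can reach only ABR counts that include untreated bleeds, and the size of that effect is also unknown. This is a gap in the wording of a safety-primary protocol that is cheap to close. It is not evidence that serious toxicity would be missed.

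**What to change.** In Protocol Section 9.6.1:

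- Limit the exemption to non-serious bleeds attributed to hemophilia.
- State that bleeding or hematoma at the injection site is documented as an AE and counted as an ISR, and is identified as such so that it is not also counted as a hemophilic bleed.
- State that a non-serious bleed with another suspected cause, including the study drug, is documented as an AE with causality and CTCAE grade, in addition to the diary entry.

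Add one sentence to the SAP so that identified injection-site bleeds go to the ISR table and stay out of the hemophilic bleed counts and ABR. Reconcile Section 9.6.1 with Sections 9.6.1.1, 9.6.1.2.3, 9.6.1.6 and 9.6.1.7.

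The cost is a few sentences, a few more AE pages, and AE and ISR incidences that may look slightly less favourable. More events may also count toward the existing trigger in Section 9.6.1.7. The sponsor and the DMC should know this when the wording changes.
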